A Phase 2b, international, multicenter, randomized, double-blind, placebo-controlled, dose-ranging, efficacy, and safety study (Study PTC124-GD-007-DMD; Study 007) evaluating ataluren in patients with nmDBMD was conducted. Patients were 5 to 20 years of age and were ambulatory at baseline. They were randomized 1:1:1 to receive placebo; ataluren at a low dose of 10 mg/kg (morning), 10 mg/kg (midday), 20 mg/kg (evening); or ataluren at a high dose of 20 mg/kg (morning), 20 mg/kg (midday), 40 mg/kg (evening). Patients completing this study continued to receive high-dose ataluren in an open-label extension to this study (PTC124-GD-007e-DMD; Study 007e). The safety data from Study 007 revealed a favorable ataluren safety profile across both ataluren dose levels. Efficacy data indicated that patients receiving low-dose ataluren experienced a slower loss of walking ability relative to patients receiving placebo. Efficacy in the high-dose ataluren arm was not better than observed in the placebo arm. Given these data suggesting the potential for an inverse dose-response relationship favoring the lower dose of ataluren, the data monitoring committee (DMC) for the ataluren DBMD program recommended discontinuation of ongoing studies evaluating high-dose ataluren. Consequently, ataluren administration in the open-label extension studies (004e and 007e) and in an additional

open-label study assessing the safety and exposure profiles of ataluren in nonambulatory patients with nmDBMD (Study PTC124-GD-008-DMD; Study 008) was halted in March 2010.

At the end of Study 007 (Week 48), the mean change from baseline in 6-minute walk distance (6MWD) was ~30 meters greater in patients treated with low-dose ataluren than in patients treated with placebo, consistent with the 30-meter change specified in the study protocol as being clinically relevant. The improvement among patients treated with low-dose ataluren compared to patients treated with placebo was generally consistent regardless of age, use of corticosteroids, or walking ability at the beginning of the study. There was no difference between high-dose ataluren and placebo in change in 6MWD over 48 weeks.

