1.2. Study Design

This study comprises a Phase 3, open-label study of ataluren in patients with nmDBMD who previously received ataluren at an investigator site in a prior PTC-sponsored clinical study. A separate open-label study (PTC124-GD-016-DMD) is being conducted for nmDBMD patients who previously received ataluren at an investigator site in the United States (US).

All participating sites must have had at least 1 patient that received at luren treatment in a prior PTC-sponsored clinical study in DBMD. It is planned that up to ~96 patients will be enrolled.

Subjects will receive ataluren 3 times per day (TID) at respective morning, midday, and evening doses of 10 mg/kg, 10 mg/kg, and 20 mg/kg, for approximately 240 weeks. Study assessments will be performed at clinic visits during screening, on the first day of ataluren dosing, and then every 12 weeks during the ataluren treatment period.

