2.2.3.2.3. Other Completed Studies

Subjects completing Study 007 were eligible to enroll in an open-label extension trial PTC124-GD-007e-DMD (Study 007e). Of the 174 patients participating in the blinded Phase 2b study, 173 patients enrolled in this study. These patients received the 20-, 20-, 40-mg/kg dose level of ataluren for a median [range] of 22 [11 to 57] weeks before the study was discontinued on 03 March 2010. The safety findings from this study confirmed that ataluren was well tolerated; there were no concerning safety signals evident in the patients participating in this trial.

Subjects completing Study 004 were eligible to enroll in an open-label extension trial. Of the 38 patients participating in the prior Phase 2a study, 36 patients enrolled in an open-label extension study PTC124-GD-004e-DMD (Study 004e). These patients received the 20-, 20-, 40-mg/kg dose level of ataluren for a median [range] of 70 [53 to 81] weeks before the study was discontinued on 03 March 2010. The safety results from this trial also documented good tolerability for ataluren; there were no worrisome ataluren-related adverse events reported for the patients participating in this trial.

In addition, an open-label Phase 2a study PTC124-GD-008-DMD (Study 008) was conducted in nonambulatory patients with nmDBMD; this study was discontinued on 03 March 2010. At the time of discontinuation, 6 patients had received the 20, 20, 40 mg/kg dose level of ataluren for periods ranging from1 week to 6 weeks. While no safety concerns were identified during this study, with the small number of patients and short duration of dosing, no definitive conclusions can be drawn from this study regarding the safety profile of ataluren 20, 20, and 40 mg/kg in nonambulatory boys with nmDBMD.

The results of the nmDBMD program were reviewed by an independent DMC on 24 February 2010. It was the DMC opinion that there were no safety concerns based on the available data.

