2.2.3.2.4. Ongoing Studies

A Phase 3 open-label, study PTC124-GD-016-DMD (Study 016) to assess the safety of ataluren in patients who participated in one of the 5 previous ataluren nmDBMD studies at an investigator site in the US is ongoing. As of 01 September 2015, this study had enrolled 108 patients who

received ataluren for a median of 227 weeks (range, 4 to 249 weeks). To date in this study, ataluren has been well tolerated. Further details on the safety results are found in the IB.

A Phase 3 extension study (Study 020e) of ataluren (PTC124) in patients with nonsense mutation dystrophinopathy, that is being conducted at 54 sites in 18 countries. As of 31 July, 2015, this study had enrolled 199 patients who received ataluren for a median of 24 weeks (range, 0.2 to 71 weeks). To date in this study, ataluren has been well tolerated. Further details on the safety results are found in the IB.

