6.4.3. Cardiac Drugs for CHF Prophylaxis/Treatment

Cardiac drugs (eg, ACE inhibitors, ARBs, beta-blockers, etc) may be used in the treatment of congestive heart failure (CHF) in nonambulatory patients with DMD and may increasingly be considered for use as prophylaxis against symptomatic cardiac dysfunction in younger boys with the disease [Bosser 2004, American Academy of Pediatrics 2005, Duboc 2005, Kajimoto 2006, Ramaciotti 2006].

In patients who are receiving an ACE inhibitor or ARB, monitoring of plasma renin and aldosterone values in patients with treatment-emergent evidence of adrenal dysfunction should be conducted with the understanding that high renin values or low aldosterone values may not

represent definitive evidence of adrenal toxicity. In patients on these drugs who develop other evidence for primary adrenal insufficiency (eg, elevated plasma ACTH concentration), reassessment of plasma renin and aldosterone after interruption of ACE inhibitor or ARB treatment may be warranted.

Subjects who require initiation, interruption, dose modification, or reinstitution of CHF prophylaxis/treatment may continue ataluren dosing.

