7.2.21. Disease Status Survey

For all patients, a disease status survey will be administered at Screening (Visit 1) to collect retrospective information on patient and/or parent-reported changes in disease status during and after their participation in the prior PTC Therapeutics Studies 007 and 007e.

A separate survey will be administered at Week 1 (Visit 2), Week 12 (Visit 3), Week 24 (Visit 4), Week 36 (Visit 5), Week 48 (Visit 6), Week 60 (Visit 7), Week 72 (Visit 8), Week 84 (Visit 9), Week 96 (Visit 10), Week 108 (Visit 11), Week 120 (Visit 12), Week 132 (Visit 13), Week 144 (Visit 14), Week 156 (Visit 15), Week 168 (Visit 16), Week 180 (Visit 17), Week 192 (Visit 18), Week 204 (Visit 19), Week 216 (Visit 20), Week 228 (Visit 21), Week 240 (Visit 22 End-of-Treatment/Premature Discontinuation) to collect prospective information on patient and/or parent-reported changes in disease status.

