8.2 Matched Populations

To compare CINRG with Study 019, the matched populations are defined in the following table for different endpoints and analyses. Matching criteria will be adjusted if imbalance demographics and baseline characteristics are observed.

Endpoint/ Analysis	Age (Years) at Study Entry	Age (Years) at Assessment	Steroid Use	Ambulation status	Exclude EXON 51 and 45	Baseline value	Visit Year
Age at loss of ambulation	9-18	Not applicable	Cumulative Steroid use duration at study entry ≥ 12 months	Ambulatory at study entry	Yes	time taken to run/walk 10 meters 3.5-26.4 seconds ²	Not applicable
Age at FVC <1 liter	9-18	Not applicable	Not applicable	Non- ambulatory at study entry	Yes	1-3.08	Not applicable
Piece-wise regression based on FVC	Not applicable	≤ 22	Cumulative Steroid use duration at each assessment ≥ 24 months	Non- ambulatory at each assessment	Yes	Not applicable	≥ 2012
%- predicted FVC	9-21	Not applicable	Not applicable	Non- ambulatory at study entry	Yes	32.6- 110.3	Not applicable
%- predicted FEV1	9-21	Not applicable	Not applicable	Non- ambulatory at study entry	Yes	28.1- 104.0	Not applicable
PEF	9-21	Not applicable	Not applicable	Non- ambulatory at study entry	Yes	1.3-218.0	Not applicable
EK	9-18	Not applicable	Not applicable	Ambulatory at study entry	Yes	Score 0-15	Not applicable
6MWT	9-18	Not applicable	Cumulative Steroid use duration at study entry ≥ 12 months s	Ambulatory at study entry	Yes	36-553 meters	Not applicable
time taken to run/walk 10 meters	9-18	Not applicable	Cumulative Steroid use duration at study entry ≥ 12 months	Ambulatory at study entry	Yes	3.5-26.4 seconds	Not applicable
time taken to stand from supine	9-18	Not applicable	Cumulative Steroid use duration at study entry ≥ 12 months	Ambulatory at study entry	Yes	2.3-30 seconds	Not applicable
NSAA	9-18	Not applicable	Cumulative Steroid use duration at study entry ≥ 12 months s	Ambulatory at study entry	Yes	Total score 3-34	Not applicable

8.2.1 Analyses Based on Matched Populations of CINRG and Study 019

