Demographics and baseline characteristics (age, race, ambulation status, corticosteroid use (yes or no), duration of corticosteroid use, corticosteroid type, baseline 6MWD, baseline time to run/walk 10 meters, baseline time to stand from supine, baseline %-predicted FEV1, %-predicted FVC, PEF, EK score, NSAA total score) will be summarized descriptively for CINRG and Study 019 based on each matched population. The summary will be displayed by corticosteroid use (yes vs no) and cumulative steroid use (≥ 12 months vs < 12 months) for baseline ambulatory and non-ambulatory subjects separately. In general, the baseline is defined as the first visit in CINRG data. The baseline age in the FVC analysis using piece-wise regression models is the age at the first FVC assessments for both CINRG and Study 019.

The comparison to the natural history data (ie, CINRG data) based on matched subjects will be performed in FVC using piece-wise regression models, age to loss of ambulation, and age to FVC < 1 liter using Kaplan-Meier method.

Piece-wise regression models will be applied to log FVC in CINRG and Study 019 data, separately, using different ages as the changepoint. The most possible changepoint in terms of age will be chosen at the best model fit (ie, AICC value is the maximal). Scatter plots of log FVC and the most fitted piece-wise regression line will be generated for CINRG and Study 019, separately. Comparison between the observed and predicted FVC in Study 019 will be performed using repeated measures analysis of variance to account for within-subject correlation, where the predicted values are based on the regression equation estimated by the best fit regression model based on CINRG data.

The Kaplan-Meier method will be applied to the analysis of age to loss of ambulation and age to FVC < 1 liter. The median age to loss of ambulation and median age to FVC < 1 liter will be reported. The comparison between Study 019 and CINRG will be conducted via log-rank test by corticosteroid use at baseline (yes or no) and overall. The Kaplan-Meier curves will also be displayed.

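### The two log-rank comparisons with the CINRG registry have no calendar limit and no check on calendar year, although all Study 019 follow-up appears to fall after March 2010

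*Protocol*

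**What the plan says.** **Timing of Study 019.** Protocol 1.1 reports that ataluren dosing in Studies 004e, 007e and 008 "was halted in March 2010". Protocol 2.2.3.2.3 adds that Study 007e patients were treated "for a median [range] of 22 [11 to 57] weeks before the study was discontinued on 03 March 2010". Study 019 takes patients "who previously received ataluren at an investigator site in a prior PTC-sponsored clinical study" (Protocol 1.2). Its screening survey asks about disease status "during and after their participation in the prior PTC Therapeutics Studies 007 and 007e" (Protocol 7.2.21).

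**Matching to CINRG.** The table in SAP 8.2 has eleven rows and a visit-year column. One row, "Piece-wise regression based on FVC", requires 2012 or later. The other ten are marked not applicable, including age at loss of ambulation and age at FVC below 1 liter.

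**The tests.** For those two endpoints SAP 8.2.1 states: "The comparison between Study 019 and CINRG will be conducted via log-rank test by corticosteroid use at baseline (yes or no) and overall". SAP 8.1 gives the purpose of the CINRG control as assessing ataluren's long-term benefit.

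**Baseline and balance.** SAP 8.2.1 generally takes CINRG baseline as a boy's first registry visit. Its list of characteristics to be summarised for each matched population has no calendar variable. SAP 8.2 allows the matching to be adjusted if demographics or baseline characteristics turn out to be imbalanced.

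**The concern.** An external control is informative only if the two cohorts would have progressed alike without the drug, and shared calendar time is part of that. Study 019 is bound to the period after March 2010. Nothing in the SAP binds the log-rank controls to the same period, and nothing would show whether they come from it. The fallback on matching cannot catch a calendar imbalance, because calendar year is not among the characteristics to be summarised.

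If some CINRG follow-up is older, and boys followed earlier lost ambulation or lung function at younger ages because of the care of that time, the log-rank test would credit that gap to ataluren. These are the SAP's between-cohort time-to-event tests of benefit, and as log-rank tests they have no covariate adjustment.

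**Working it through.** **1. Is Study 019 follow-up all after March 2010?** The documents give no first-dose date, so this is an inference.
- Dosing in the earlier extension studies stopped in March 2010. Study 019 re-treats exposed boys and asks them at screening about the time during and after 007/007e.
- Indirect check from the sister US study: at 01 September 2015, patients in Study 016 had "received ataluren for a median of 227 weeks (range, 4 to 249 weeks" (Protocol 2.2.3.2.4). 01 September 2015 minus 249 weeks is 23 November 2010, so no exposure counted there began earlier.
- From 03 March 2010 to 01 January 2012 is 669 days, or 95.6 weeks. A 2012 limit may therefore be later than the true start of Study 019.

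**2. Which SAP 8.2 rows are limited by year, and how are they defined?**

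| Row | Criteria applied at | Steroid criterion | Visit year | Comparison in SAP 8.2.1 |
|---|---|---|---|---|
| Piece-wise FVC | each assessment | ≥24 months | ≥2012 | regression |
| Age at loss of ambulation | study entry | ≥12 months | none | log-rank |
| Age at FVC <1 liter | study entry | none | none | log-rank |

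Visit year was thus available as a criterion. The filter on the first row would do nothing unless the data for that analysis held visits before 2012. How many there are, and whether they bear on the log-rank sets, is not stated.

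**3. How much could a period effect matter?** There is no stated event count, power or significance level to reproduce, so every value here is assumed: two-sided 0.05 (2.5% in ataluren's favour), no drug effect, *d* total events, a share *p* of patients in one cohort, and a hazard ratio *h* caused by period alone. The Schoenfeld approximation gives

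P(significant for ataluren) = Φ(√(*d·p*(1−*p*)) × |ln *h*| − 1.96).

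Worked case: *d* = 60, *p* = 0.5, *h* = 0.8. √15 = 3.873; 3.873 × 0.2231 = 0.864; 0.864 − 1.96 = −1.096; Φ(−1.096) = 13.7%.

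| *h* from period alone | Lowest (*d* = 30, *p* = 0.3) | Highest (*d* = 100, *p* = 0.5) |
|---|---|---|
| 1.0 | 2.5% | 2.5% |
| 0.9 | 4.5% | 7.6% |
| 0.8 | 8.1% | 19.9% |
| 0.7 | 14.4% | 43.0% |

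**4. The same question in years of age.** Simulation with assumed values: 50 Study 019 and 150 CINRG boys, age at loss normal with mean 14 and SD 2.5 years, and half or all of the controls shifted earlier. The simple version has uniform censoring at ages 12-19. The second version requires each boy to be event-free at an entry age uniform on 9-15, followed for 0.5 to 4.6 years. Entries are the chance of a significant result for ataluren with half / all controls shifted.

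| Shift | No entry condition | Event-free at entry |
|---|---|---|
| 0.5 year | about 7% / 17% | about 4% / 11% |
| 1 year | about 16% / 55% | about 8% / 26% |

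At a shift of 0.25 year the second version gives 3-4%, close to nominal. The SAP's requirement to be ambulatory at entry therefore removes a good part of the effect. Matching on baseline function, not modelled here, could remove more.

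**The case against.** **No old controls are shown.** A reader might infer that the controls come from an earlier era and that the comparison is therefore biased towards ataluren. The documents do not support this: they give no CINRG calendar range, visit dates or counts. This stands, and the point must remain conditional.

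**No relevant trend in care is shown.** Protocol 6.4.3 says that cardiac drugs "may increasingly be considered for use as prophylaxis against symptomatic cardiac dysfunction in younger boys with the disease", but that concerns the heart, not walking or FVC. A bibliography title on life expectancy since 1967 concerns survival. Protocol 1.1 names chronic corticosteroids as the only treatment that has slowed progression. Steroid use is partly handled: the ambulation row requires at least 12 months of use at entry, and both tests are also run by baseline use. This mitigation is real but incomplete. The FVC <1 liter row has no steroid criterion, and neither step covers other care.

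**The rows differ in kind.** A reader might infer that the SAP contradicts itself by barring FVC readings from before 2012 in one analysis and accepting them in another. That goes too far. The piece-wise row is defined assessment by assessment, where a visit-year filter fits directly. The log-rank rows are defined by subject at entry, where it needs a new entry rule. The difference may reflect the unit of analysis, although the SAP gives no reason for it.

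**The obvious repair has its own bias.** Restarting CINRG boys in 2012 removes those who already had the event. Without delayed-entry risk sets this selects slow progressors and can work against ataluren. This stands, and is why the main comparison should not simply be replaced.

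**The stakes are limited.** The primary objective is safety, and CINRG is an addition to the protocol-defined analyses. Even so, SAP 8.1 uses it to assess benefit.

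**Conclusion.** The gap is real and limited. The SAP does nothing to make the log-rank controls contemporaneous with Study 019 and nothing to show whether they are. It follows only that a period effect could contribute to a difference favouring ataluren, if CINRG supplies earlier follow-up and if care for these endpoints improved. The documents establish neither condition, nor the size or direction of a trend.

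The false-positive rates above are illustrative. A small drift (hazard ratio 0.9, or 0.25 year) leaves the rate at roughly 3-8%; a sizeable one would matter. The 55% figure needs every control to be a full year earlier with no entry condition, and should not be quoted as an estimate for this trial. That Study 019 follow-up falls after March 2010 is a firm inference, not a stated date. The point merits a cheap addition to the SAP, not a new main analysis.

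**What to change.** 1. Keep the main log-rank comparisons as planned.
2. In SAP 8.2.1, add calendar year of entry, for both cohorts, to the summary of each matched population.
3. Prespecify a sensitivity log-rank test for age at loss of ambulation and for age at FVC <1 liter, restricted to CINRG follow-up in or after 2012, or in or after the year of first Study 019 dosing. Choose the year and state the reason before the comparison is run.
4. In that analysis, let each boy in either cohort enter the risk set at his age at his first eligible event-free visit (delayed entry). Amend the CINRG baseline definition for this analysis only, since a first registry visit may precede the window.

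The cost is SAP wording and one more run, using a variable and a cut-off the SAP already has. Fewer CINRG boys and less follow-up will widen the intervals, in the sensitivity analysis only. How many boys would be lost cannot be computed from the documents. If the restriction removes all drift and no other bias is present, the chance of a false result for ataluren returns to the nominal 2.5% per comparison under the assumed two-sided 0.05.

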2.2.3.2.4. Ongoing Studies

A Phase 3 open-label, study PTC124-GD-016-DMD (Study 016) to assess the safety of ataluren in patients who participated in one of the 5 previous ataluren nmDBMD studies at an investigator site in the US is ongoing. As of 01 September 2015, this study had enrolled 108 patients who

received ataluren for a median of 227 weeks (range, 4 to 249 weeks). To date in this study, ataluren has been well tolerated. Further details on the safety results are found in the IB.

A Phase 3 extension study (Study 020e) of ataluren (PTC124) in patients with nonsense mutation dystrophinopathy, that is being conducted at 54 sites in 18 countries. As of 31 July, 2015, this study had enrolled 199 patients who received ataluren for a median of 24 weeks (range, 0.2 to 71 weeks). To date in this study, ataluren has been well tolerated. Further details on the safety results are found in the IB.

2.2.3.3. Safety Experience in Other Indications

Ataluren is also being evaluated in children and adults with other nonsense mutation genetic disorders Safety information from other indications are provided in the Ataluren Investigator Brochure.

3. STUDY OBJECTIVE AND ENDPOINTS

3.1. Primary Objective

The primary objective of this study is to assess the long-term safety and tolerability of 10, 10, 20 mg/kg ataluren in patients with nmDBMD who had prior exposure to ataluren in a PTC-sponsored clinical trial.

3.2. Secondary Objectives

Secondary objectives include the following:

- Ambulatory patients (able to run/walk 10 meters in ≤30 seconds) To determine the effect of ataluren on ambulation and other aspects of physical function
- Nonambulatory patients (unable to run/walk 10 meters in ≤30 seconds) To assess the effect of ataluren on activities of daily living, upper limb function, and pulmonary function
- All patients To assess patient and/or parent/caregiver reports of changes in disease status:
 - Retrospectively during and after participation in previous studies (Studies 007 and 007e)
 - o Prospectively during the current study

3.3. Clinical Endpoints

Primary

• Safety profile characterized by type, frequency, severity, timing, and relationship to ataluren of any adverse events or laboratory abnormalities

Secondary

• In ambulatory patients, change from baseline in 6MWD as measured by the 6-minute walk test (6MWT)

- In ambulatory patients, change from baseline in physical function as measured by the North Star Ambulatory Assessment (NSAA)
- In ambulatory patients, change from baseline in timed function tests (time to stand from supine and time to run/walk 10 meters)
- In nonambulatory patients, change from baseline in pulmonary function as measured by spirometry
- In nonambulatory patients, change from baseline in patient and parent/caregiver-reported activities of daily living, as measured by the Egen Klassifikation (EK) scale
- In all patients, changes in patient and/or parent/caregiver reports of disease status as measured by a standardized survey administered by site personnel

